# 8.1.3 Day 7/Visit 3 (±1 day)

The Investigator or designee will:

1. Ask the subject about AEs using an open-ended question, such as "Have you noticed any change in your health since the last visit?" Record all events, as appropriate.

- 2. Ask the subject about any changes in his/her concomitant therapies/procedures (added, removed or changed) since the previous visit. Record all changes.
- 3. CCI
- 4. Instruct subject on how to complete the SLA at maximum frown. Subject to complete GL-SLA at maximum frown using the Static 4-point Categorical Scale (Section 7.1.2).
- 7. Obtain the subject's vital signs (blood pressure, heart rate, and respiratory rate). Vital signs are to be taken seated after 10 minutes rest (Section 7.2.2).
- 8. Take subject photographs (refer to photo manual for complete instructions). If the subject is wearing make-up, instruct the subject to remove it prior to taking photographs.
- 9. Investigator to complete assessment of the subject's glabellar line severity at CCI maximum frown using the 4-point Photographic Scale (GL-ILA) (Section 7.1.1 and Appendix 1).
- 10. Investigator to perform a focused PE (Appendix 5).
- 11. Schedule the next visit (Day 14  $\pm$ 3 days).

### 8.1.4 Day 14/Visit 4 (±3 days)

The Investigator or designee will:

- 1. Ask the subject about AEs using an open-ended question, such as "Have you noticed any change in your health since the last visit?" Record all events, as appropriate.
- 2. Ask the subject about any changes in his/her concomitant therapies/procedures (added, removed or changed) since the previous visit. Record all changes.
- 3. Instruct subject on how to complete the SLA at maximum frown. Subject to complete GL-SLA at maximum frown using the Static 4-point Categorical Scale (Section 7.1.2).

- 6. Obtain the subject's vital signs (blood pressure, heart rate, and respiratory rate). Vital signs are to be taken seated after 10 minutes rest (Section 7.2.2).
- 7. Take subject photographs (refer to photo manual for complete instructions). If the subject is wearing make-up, instruct the subject to remove it prior to taking photographs.

- 8. Investigator to complete assessment of the subject's glabellar line severity at maximum frown using the 4-point Photographic Scale (GL-ILA) (Section 7.1.1 and Appendix 1).
- 9. Investigator to perform a focused PE (Appendix 5).
- 10. Schedule the next visit (Month  $1 \pm 5$  days).

### 8.1.5 Month 1/Visit 5 (±5 days)

The Investigator or designee will:

- 1. Ask the subject about AEs using an open-ended question, such as "Have you noticed any change in your health since the last visit?" Record all events, as appropriate.
- 2. Ask the subject about any changes in his/her concomitant therapies/procedures (added, removed or changed) since the previous visit. Record all changes.
- 3. Instruct the subject on how to complete the SLA at maximum frown. Subject to complete GL-SLA at maximum frown using the Static 4-point Categorical Scale (Section 7.1.2).

- 8. Obtain the subject's vital signs (blood pressure, heart rate, and respiratory rate). Vital signs are to be taken seated after 10 minutes rest (Section 7.2.2).
- 9. Obtain 12-lead ECG recording after the subject has been resting in a supine position for at least 10 minutes (Section 7.2.3).
- 10. Collect blood sample for neutralizing antibody testing.
- 11. Take subject photographs (refer to photo manual for complete instruction). If the subject is wearing make-up, instruct the subject to remove it prior to taking photographs.
- 12. Investigator to complete assessment of the subject's glabellar line severity at maximum frown using the 4-point Photographic Scale (GL-ILA) (Section 7.1.1 and Appendix 1).
- 13. Investigator to perform a focused PE (Appendix 5).
- 14. Schedule the next visit (Month  $2 \pm 5$  days).

### 8.1.6 Months 2-5/Visit 6-9 (±5 days)

The Investigator or designee will:

- 1. Ask the subject about AEs using an open-ended question, such as "Have you noticed any change in your health since the last visit?" Record all events, as appropriate.
- 2. Ask the subject about any changes in his/her concomitant therapies/procedures (added, removed or changed) since the previous visit. Record all changes.
- 3. Instruct subject on how to complete the SLA at maximum frown. Subject to complete GL-SLA at maximum frown using the Static 4-point Categorical Scale (Section 7.1.2).

- 7. Take subject photographs (refer to photo manual for complete instructions). If the subject is wearing make-up, instruct the subject to remove it prior to taking photographs.
- 8. Investigator to complete assessment of the subject's glabellar line severity at maximum frown using the 4-point Photographic Scale (GL-ILA) (Section 7.1.1 and Appendix 1).
- 9. Schedule the next monthly visit ( $\pm$  5 days).

#### 8.1.7 Month 6/Visit 10 or Early Termination visit (±5 days)

At the Final/ET, the Investigator or designee will:

- 1. Ask the subject about AEs using an open-ended question, such as "Have you noticed any change in your health since the last visit?" Record all events, as appropriate.
- 2. Ask the subject about any changes in his/her concomitant therapies/procedures (added, removed or changed) since the previous visit. Record all changes.
- 3. Instruct subject on how to complete the SLA at maximum frown. Subject to complete GL-SLA at maximum frown using the Static 4-point Categorical Scale (Section 7.1.2).

CONFIDENTIAL Page 58 of 84

# 7.

- 8. Obtain the subject's vital signs (blood pressure, heart rate, and respiratory rate). Vital signs are to be taken seated after 10 minutes rest (Section 7.2.2).
- 9. Obtain 12-lead ECG recording after the subject has been resting in a supine position for at least 10 minutes (Section 7.2.3).
- 10. Collect blood sample (chemistry and hematology) for analysis at the central laboratory.
- 11. Collect blood sample for neutralizing antibody testing.
- 12. Take subject photographs (refer to photo manual for complete instructions). If the subject is wearing make-up, instruct the subject to remove it prior to taking photographs.
- 13. If the subject is a female of childbearing potential, collect urine for UPT and complete pregnancy test (see laboratory manual for additional procedures). Document the result.
- 14. Investigator to complete assessment of the subject's glabellar line severity at maximum frown using the 4-point Photographic Scale (GL-ILA) (Section 7.1.1 and Appendix 1).
- 15. Investigator to perform a focused PE (Appendix 5).
- 16. Exit the subject from the study.

# 8.2 Unscheduled Visits

When necessary, unscheduled visits may be conducted, in particular if an AE occurs and needs to be assessed and/or treated.

# 8.3 Subject Instructions

Subjects will be advised that any facial make-up will need to be removed before taking study photographs.

Subjects will also be advised of post-treatment care instructions as outlined in Section 6.1.7.2.

# 9. STATISTICAL METHODS PLANNED

# 9.1 Statistical and Analytical Plans

A Statistical Analysis Plan (SAP) will be developed as a separate document. The SAP will contain a more detailed and technical description of specific data conventions, calculations and of statistical

CONFIDENTIAL Page 59 of 84

**MA-39956** 

procedures for executing the analyses that are specified in the sections of the clinical study protocol below. The SAP will be finalized prior to database lock.

A separate SAP for EU will be created. The EU SAP will include a responder definition for the primary endpoint according to the EU requirement.

Any change made to the finalized SAP will be documented in the Clinical Study Report (CSR).

#### 9.1.1 **Data Transformations**

For antibody testing results, log transformation might be used as necessary.

#### 9.1.2 **Populations Analyzed and Evaluability**

The statistical analyses will be performed based on the following subject populations.

#### 9.1.2.1 Modified Intent-to-treat (mITT) Efficacy Population

The modified Intention-to-treat (mITT) population includes all subjects who are randomized and dispensed the investigational product, and will be analyzed according to the randomization scheme; subjects with a photographic and categorical scale Month 1 assessment via a remote visit will be excluded from the mITT. The mITT population will be used for primary efficacy analysis.

#### 9.1.2.2 Intent-to-treat (ITT) Efficacy Population

The Intention-to-treat (ITT) population includes all subjects who are randomized and dispensed the investigational product, and will be analyzed according to the randomization scheme. All secondary variables will be analyzed based on the ITT population, as well as a efficacy CC sensitivity analysis of the primary efficacy endpoint.

#### 9.1.2.3 **Per-protocol (PP) Efficacy Population**

The Per Protocol (PP) population is a subset of the mITT subjects who have no protocol deviations that are considered to have a substantial impact on the primary efficacy outcome. If the PP population contains less than 90% of the subjects in mITT, a sensitivity analysis of the primary efficacy endpoint will be performed based on the PP population.

# 9.1.2.4 Safety Population

The safety population includes all subjects who were administered the study product, and will be analyzed according to as-treated principle. All safety data will be summarized descriptively based on the safety population.

# 9.1.2.5 Imputation of Missing Data

The Observed Cases (OC) will be used for all safety analyses as well as the secondary efficacy analyses. The primary efficacy analysis will be performed using multiple imputation (MI), and repeated using baseline observation carried forward (BOCF) for missing values. If deemed necessary, any analyses may be repeated using OC, BOCF, or MI as appropriate.

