### SCHEDULE OF ASSESSMENTS

#### Table 2Schedule of Assessments

1  month = 4  weeks/28  days	Visit 1	Visit 2	Visit 3	Visit 4	Visit 5	Visit 6	Visit 7	Visit 8	Visit 9	Visit 10
All visit windows are calculated from Baseline/Day 0	Screening 	Baseline/Day 01	Day 7	Day 14	Month 1	Month 2	Month 3	Month 4	Month 5	Month 6/ET 
		(mithin 2 much a floor	(114)		(15.1.)					(15.1)
		(within 2 weeks after screening)	(±1 day)	$(\pm 3 \text{ days})$	(±5 days)					
Informed Consent	Х									
Demographic Data  including, Fitzpatrick skin type, medical										
history & concurrent diseases, previous facial	Х									
treatments/procedures (toxin naïve/non-toxin naïve)										
Inclusion /Exclusion Criteria	Х	$X^4$								
Concomitant Therapies/ Procedures	Х	X 	Х	Х	Х	Х	Х	Х	Х	Х
Adverse Events	Х	X 	Х	Х	Х	Х	Х	Х	Х	Х
Urine Pregnancy Test 	Х	$X^4$								Х
Vital Signs (blood pressure, heart rate, and respiratory rate) 		X 	Х	Х	Х					Х
ECG		$X^4$			Х					Х
Blood sample clinical chemistry and hematology		$X^4$								Х
Blood sample for serum antibody testing		$X^4$			Х					Х
ILA of GL Severity	Х	$X^4$	Х	Х	Х	X	Х	Х	Х	X
Focused Physical Examination (face, head, neck) 	Х	$X^4$	Х	Х	Х					X
Photography		$X^4$	Х	Х	Х	X	Х	Х	Х	X
Randomization		$X^4$								
Treatment		X 								
CCI										
Subject Assessments										
SLA of GL Severity 	Х	$X^4$	Х	Х	Х	Х	Х	Х	Х	Х
CCI										

1. Screening and baseline visits may be on the same day. If completed on the same day, only perform study assessments once (i.e., PE, UPT, SLA, ILA, AE, concomitant therapies/procedures, inclusion/exclusion review).

- 2. If the subject withdraws before the final visit the assessments at Month 6/ET should be completed, if possible.
- 3. Includes date of birth, gender, race, ethnicity, height, weight.
- 4. To be performed before treatment.
- 5. Performed before treatment and post-treatment.
- 6. Females of childbearing potential
- 7. Vital signs are taken seated after 10 minutes rest. Vital signs are taken prior to any blood draw (excluding post-treatment measurements on Day 0).
- 8. Post-baseline, events suggestive of remote spread of toxin are also considered while doing clinical evaluations based on the subject's symptoms and signs. Directed questioning and examination will then be performed as appropriate.

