### 9.1.5 Inferential Statistical Analyses

The primary efficacy endpoint will be a composite responder rate based on the GL-ILA and GL-SLA assessments of glabellar line severity at maximum frown at Month 1. Responder is defined as a subject who achieves a score of 0 or 1 and at least 2 grades improvement from baseline, on both scales concurrently. The null hypothesis of no relationship between treatment and responder rate will be tested against the alternative hypothesis that there is a relationship between treatment and responder rate. The responder rates of the QM1114-DP and placebo will thus be compared using Cochran-Mantel-Haenszel test, stratified by center, at 5% significance level (2-sided). Depending on the number of centers, pooling of centers might be needed. For the primary efficacy endpoint, consistency of the results will be analyzed using Cochran-Mantel-Haenszel test stratified by gender, baseline ILA, prior use of botulinum toxin, and Fitzpatrick skin type, respectively.

The analysis of the primary efficacy endpoint will be based on the mITT population. A sensitivity analysis of the primary efficacy endpoint will be performed using the ITT population.

For the secondary endpoints, the Cochran-Mantel-Haenszel test will be used to compare the proportion of subjects who achieve 0 or 1 on the GL-ILA at maximum frown at Month 1 and at all the rest of the post-treatment visits. To control the type I error rate, the fixed sequence testing procedure will be used, which requires no adjustment to the level of significance. However the comparisons must be made in a pre-specified order following the procedure outlined below:

1. Primary analysis

Secondary analysis:

- 2. Month 1
- 3. Day 14
- 4. Month 2
- 5. Month 3
- 6. Month 4
- 7. Month 5
- 8. Month 6
- 9. Day 7

If one of the tests in the sequence is not significant (p > 0.05), no confirmatory claims can be made based on tests following (and including) that one.

The secondary analysis in the sequence will be based on the ITT population with the remote visit assessments excluded. A sensitivity analysis will be run using the ITT population including the remote visit assessments.

CC

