# 12. Summary of Changes in Clinical Study Protocol 43QM1602

# 12.1 Protocol Version 3.0 to Version 4.0

Remote assessment procedures for efficacy and safety endpoints to ensure safety and respect localized and elective restrictions were implemented due to COVID-19 pandemic. Therefore, the modified Intention-to-treat (mITT) efficacy population is added to the statistical analyses for primary efficacy analysis. This action affect several sections of the Protocol as summarized below.

Section in the clinical study protocol	Rational for changes	Description of changes
Section 9.1.1, Data Transformations	Clarification	CCI
Section 9.1.2.1, Populations Analyzed and Evaluability; List of abbreviations and definitions of terms	Due to COVID-19 pandemic actions. The mITT efficacy population will be used for assessment of the primary efficacy endpoint. Subjects with a photographic and categorical scale Month 1 assessment via a remote visit will be excluded from the mITT	Modified Intent-to-treat (mITT) Efficacy Population added (primary efficacy analysis).
Section 9.1.2.2, Intent to treat (ITT) Efficacy Population	Due to COVID-19 pandemic actions.	The mITT population will be used for primary efficacy analysis. A sensitivity analysis of the primary efficacy endpoint will be based on the ITT population.
Section 9.1.2.3, Per- protocol (PP) Efficacy Population	Clarification due to COVID-19 pandemic actions.	Changed from "ITT" to "mITT"
Section 9.1.2.5, Imputation of Missing Data	Due to COVID-19 pandemic actions. An increased number of drop-outs/ missing data at Month 1 visit.	Primary imputation changed to "MI" instead of "BOCF".
Section 9.1.5, Inferential Statistical Analyses	Clarification due to COVID-19 pandemic actions.	Added: "The analysis of the primary efficacy endpoint will be based on the mITT population. A sensitivity analysis of the primary efficacy endpoint will be performed using the ITT population." "The secondary analysis in the sequence will be based on the ITT population with the remote visit

MA-39956

Doc id

Section in the clinical study protocol	Rational for changes	Description of changes
		assessments excluded. A sensitivity analysis will be run using the ITT population including the remote visit assessments."

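### The eight confirmatory secondary tests rest on observed cases with no required missing-data sensitivity analysis, while the primary uses multiple imputation; at Month 1 the same missing GL-ILA score is handled two ways

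*Protocol*

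**What the plan says.** - **Secondary method.** Protocol 9.1.2.5: "The Observed Cases (OC) will be used for all safety analyses as well as the secondary efficacy analyses".
- **Primary method.** Same section: "The primary efficacy analysis will be performed using multiple imputation (MI), and repeated using baseline observation carried forward (BOCF) for missing values".
- **Optional repeats.** Same section: "If deemed necessary, any analyses may be repeated using OC, BOCF, or MI as appropriate". No trigger, endpoint or method is fixed.
- **Population.** Protocol 9.1.2.2: "All secondary variables will be analyzed based on the ITT population". Section 9.1.5 then removes remote-visit scores from the secondary sequence. The one sensitivity analysis it fixes for that sequence puts them back.
- **Status of the tests.** Section 9.1.5 orders the primary first and then eight GL-ILA tests: Month 1, Day 14, Months 2 to 6, Day 7. On stopping: "If one of the tests in the sequence is not significant (p > 0.05), no confirmatory claims can be made based on tests following".
- **Reason for MI in the primary.** The change summary in section 12.1 gives: "An increased number of drop-outs/ missing data at Month 1 visit". It records that MI took the place of BOCF.

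**The concern.** Steps 2 to 9 can each support a confirmatory claim, yet each is computed only on subjects with an on-site score at that visit. A missing score drops out, and so does a remote one. The analysis is labelled ITT, but its denominator changes from visit to visit.

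The contrast is sharpest at Month 1. GL-ILA is one of the two components of the primary composite (section 2.1.1) and the whole of the step 2 endpoint. The reason given for imputing at step 1 applies equally to the same score at step 2.

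Observed cases give unbiased rates only if, within arm, missingness is unrelated to response. There is a plausible reason to doubt that at later visits. Section 1.1 says the effect usually lasts about 4-6 months, after which severity returns to baseline. Section 5.4.5 prohibits other botulinum toxin and facial aesthetic procedures during the study, and section 5.5 lets subjects leave at any time. A subject who did not improve, or whose lines have returned, has a reason to go. The protocol gives no drop-out figures, so this is a possibility and not a finding. At stake are the late-visit response rates and, under a further condition shown below, the error rate of the late tests.

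**Working it through.** **Inputs.** From the protocol: 225 and 75 subjects (9.2.3), eight secondary tests (9.1.5), and baseline GL-ILA of 2 or 3 at maximum frown (5.2.1). The protocol as available gives no response or missingness rates, so those below are assumptions.

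**1. Count.** The secondary tests are Month 1, Day 14, Months 2, 3, 4, 5 and 6, and Day 7, which makes 8. One of them, Month 1, is at the primary's visit.

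**2. Bias in the rates with the same loss in both arms.** Let p be the true rate, and let dr and dn be the missing fractions among responders and non-responders. The observed-case rate is p(1−dr) / [p(1−dr) + (1−p)(1−dn)]. Assume 30% v 5%, with dr = 5%.

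| dn | QM1114-DP | Placebo | Difference |
|---|---|---|---|
| true | 30.0% | 5.0% | 25.0 |
| 15% | 0.285/(0.285+0.595) = 32.4% | 0.0475/(0.0475+0.8075) = 5.6% | 26.8 |
| 25% | 0.285/(0.285+0.525) = 35.2% | 0.0475/(0.0475+0.7125) = 6.3% | 28.9 |

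The overstatement is 1.8 to 3.9 points. BOCF counts every missing subject as a non-responder, because all enter at grade 2 or 3. It would give 28.5% v 4.75%, a difference of 23.75 points. In this example the two methods lie on either side of the truth.

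**3. Effect on the test in that example.** The true odds ratio is (0.30/0.70)/(0.05/0.95) = 8.14. Under observed cases with dn = 15% it is (0.285/0.595)/(0.0475/0.8075) = 8.14. The factor (1−dr)/(1−dn) cancels between arms, so a true odds ratio of 1 also stays at 1. Equal loss shifts the rates but creates no false claim.

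**4. Unequal loss under the null.** Assume a true rate of 30% in both arms, with only non-responders missing. For 20% active v 5% placebo, the rates are 0.30/(0.30+0.56) = 34.9% and 0.30/(0.30+0.665) = 31.1%, a spurious 3.8 points. An unstratified pooled two-proportion test was simulated (200,000 runs, 225 v 75, two-sided 0.05):

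| Non-responders missing, active v placebo | Spurious difference (points) | Total error | Error favouring active (nominal 0.025) |
|---|---|---|---|
| 20% v 20% | 0.0 | 0.051 | 0.024 |
| 20% v 5% | 3.8 | 0.087 | 0.081 |
| 30% v 10% | 5.7 | 0.129 | 0.127 |
| 5% v 20% | −3.8 | 0.094 | 0.006 |

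The direction depends entirely on which arm loses more non-responders.

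**5. Power cost of a BOCF repeat.** Assume 20% v 5% at a late visit, with missingness unrelated to response at 5%, 10% and 20%. Power is 0.913, 0.895 and 0.848 under observed cases, and 0.910, 0.888 and 0.833 under BOCF. The largest loss is 0.848 − 0.833 = 0.015. At 80% v 5% both are about 1.00.

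MI was not simulated, because the protocol does not give its model.

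**The case against.** Several stronger readings are tempting, and the documents do not support them.

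- **That the plan has already rejected observed cases.** It has not. MI replaced BOCF, BOCF stays as the repeat of the primary, and observed cases remain among the allowed repeats.
- **That steps 1 and 2 compare different subjects.** The mITT set omits subjects assessed remotely at Month 1, and step 2 omits remote scores, so the observed on-site subjects coincide. They differ in who is imputed. The other seven tests are at other visits.
- **That this is a completers' analysis.** Observed cases use everyone scored on site at a visit, including those who leave later.
- **That false claims follow.** With equal loss by arm they do not (step 3). No passage says that active non-responders will be lost more often.
- **That the duration claims are biased.** Duration of response is analyzed by Kaplan-Meier (9.1.3, 9.1.3.1), not from visit-wise rates.
- **That early-termination scores will count as Month 6.** Table 2 says only "If the subject withdraws before the final visit the assessments at Month 6/ET should be completed, if possible". Mapping those records to an analysis visit is a data convention that section 9.1 leaves to the SAP.

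Two further objections carry weight. Section 9.1.2.5 already permits repeats by BOCF or MI, and the SAP could fix them. However, the permission is discretionary, and the main method is set in the protocol itself. Standard MI also assumes that missingness depends on observed data, so it only partly corrects loss driven by the unseen current score. That is a reason to require BOCF beside it, not a reason to keep observed cases as the main analysis.

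**Conclusion.** The point holds as an inconsistency that is cheap to correct. Eight confirmatory tests rest on observed cases, with remote scores removed as well, and no required sensitivity analysis addresses missing values. At Month 1 the same missing GL-ILA score is imputed for one confirmatory test and discarded for the next.

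On the assumed rates, the late-visit difference is overstated by 1.8 to 3.9 points on 25. This rests on non-responders being lost three to five times as often as responders, equally in both arms. The type I error of the tests moves only if the loss differs by arm, and it could favour either the product or placebo. At a Month 1-like effect the test result would hardly be in doubt under either method. The late visits, where the effect wanes, are where the choice matters.

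**What to change.** - **Main analysis.** In 9.1.2.5 and 9.1.5, replace observed cases for steps 2 to 9 with an ITT analysis in which missing and excluded remote GL-ILA scores are multiply imputed. Use one longitudinal model consistent with the primary MI. GL-ILA is scored at every post-treatment visit (7.1.1), so each subject's other scores can inform the missing one.
- **Required sensitivity analyses.** Name observed cases and BOCF as mandatory for the sequence, and keep the existing analysis that includes remote scores. BOCF is needed because MI only partly corrects loss that depends on the unobserved score.
- **Left to the SAP.** The details of the imputation model.

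**Cost.** Wording in two protocol sections and the SAP, and some extra analysis work. The primary already needs an imputation model, though it must be extended to all visits and to subjects outside the mITT set. Late-visit rates may come out slightly less favourable.
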